## 7.1.1 Temporary Discontinuation

See Section 6.6.5.

#### 7.1.2 Rechallenge

For instructions/considerations regarding re-treatment of patients who have experienced a DLT see Sections 6.6.3.1 (Part 1A) and 6.6.3.2 (Part 1B), and for those who have experienced an IRR, see Section 6.6.4.2.

#### 7.2 Withdrawal from the Trial

Patients will be withdrawn from the trial (dose escalation or expansion) for the following reasons:

- A patient may withdraw from the trial at any time at his or her own request,
- At the discretion of the investigator for safety, behavioral, compliance, or administrative reasons,
- Lost to follow-up,
- Patient died.
- Trial closure.

If the patient withdraws consent for disclosure of future information, the sponsor may retain and continue to use any data collected before such a withdrawal of consent.

If a patient withdraws from the trial, he or she may request destruction of any samples taken and not tested, and the investigator must document this in the site trial records.

The sponsor will make any effort to ensure patients are followed up for completion of safety assessment in the trial. See Table 1-1 and Table 1-2 for data to be collected at the time of trial discontinuation and follow-up and for any further evaluations that need to be completed.

When a patient withdraws consent, the reason for withdrawal is to be documented in the eCRF and in the source document. Trial drug assigned to the withdrawn patient may not be assigned to another patient.

## 7.2.1 Withdrawal from the Use of Research Samples

The patient may withdraw their consent for future use of research samples at any time. To initiate the sample destruction process, the investigator must notify the sponsor of withdrawal of consent for the research samples and to request sample destruction. The sponsor will then initiate the process for sample destruction. If requested, the investigator will receive written confirmation from the sponsor that the samples have been destroyed. If the patient withdraws consent for research samples, the sponsor may retain and continue to use any data from samples already analyzed before such a withdrawal of consent. Samples will be destroyed after they are no longer needed for the clinical trial.

## 7.2.2 Safety Follow-up Evaluations

Patients discontinuing from treatment for any reason will have safety follow-up visits 30 days ( $\pm 5$  days) and 60 days ( $\pm 7$  days) after the patient receives the last dose of BNT411. Separate safety follow-up visits should also be done after discontinuation of atezolizumab, carboplatin and etoposide, if it occurs  $\geq 21$  days later than BNT411. If the patient initiates new anti-cancer treatment within 60 days of the last dose of trial treatment, the safety follow-up visit should be performed prior to starting new anti-cancer treatment. Once new anti-cancer treatment is initiated, the patient will move into survival follow-up.

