ECOG Performance Status 	X	X			X	X	X	X	X	X	X	X	X	X	X		X 
Adverse Events 	X	71			71	21	71	71			INUOI		A	71	71	X14	X 
Prior/Concomitant Medications and	X										NUO					X 	X 
Non-Drug Therapies 	11									0111						71	71
BNT411 Administration 		X			X	X	X	X	X	X							
End of Treatment		71			71	21	71	21	21	71			X				
New Anti-cancer Treatment													X	X	X	X	
Survival Follow-up													A	Α	A	X 	
									 				I .			A	
LABORATORY ASSESSMENTS																	
Hematology	X16	X17	X	X	X17	X17	X17	X17	X17	X17	X17	X17	X	X	X		X 
Biochemistry	X16	X17	X	X	X 	X17	X17	X 	X17	X17	X17	X 	X	X	X		X 
Coagulation factors	X 	X17			X 	X 	X17	X 	X 	X17	X 	X 	X	X	X		X 
Endocrine 	X 	X 			15		X 			X17			X				X 
Urinalysis	X 				X 		$X^{17}$	 	X 	X 	 		X	X	X		X 
Pregnancy Test 	X 	X 					inv	As ind estigate al guid	or's ass	essme	nt and	per	X	X	X		X 
Serology 16	X 										_						
PK Sampling (includes blood and	Refer to Tab	ole 1-3	for d	etails o	f PK s	amplin	gs								•	•	
urine)							-										
Tumor Biopsy, Biomarkers	Refer to Tab	ole 1-7	for d	etailed	bioma	rker ass	sessme	nt sche	dule								

1 If the patient has to go off treatment per treatment withdrawal criteria (refer Section 7.1), the treatment discontinuation visit should be performed as soon as possible after permanent discontinuation of BNT411.

- 2 Survival follow-up starts after all other protocol required visits have been completed and may be performed as telephone, email, or clinic visit.
- 3 Only if relevant or clinically indicated.
- 4 Full physical examination should be performed at screening, thereafter a limited physical examination is performed as indicated by the patient's symptoms, AEs, or other findings as determined by the investigator. Physical examination should be performed before drug administration.

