- 11 On-treatment imaging will be performed at Week 6 (+7 days), every 6 weeks (±7 days) for 48 weeks, and every 12 weeks (±7 days) thereafter until disease progression is assessed by the investigator (unless the investigator elects to continue treatment [see Section 8.5.1 for conditions of continued treatment]), withdrawal of consent, trial termination by the sponsor, or death, whichever occurs first, regardless of whether patients start a new anti-cancer therapy. Refer to Sections 10.5 and 10.6 of the protocol for RECIST 1.1. and iRECIST imaging and treatment guidelines.
- 12 ECOG status should be assessed before drug administration.
- 13 Adverse events (AEs) and serious adverse events (SAEs) should be reported from the time of signing the informed consent to 60 days (±7 days) after the patient receives the last dose of BNT411.
- 14 Suspected BNT411-related AEs only. Furthermore, in Germany only, all SAEs that occur in the patient throughout his or her lifetime should be reported refer to Table 1-5 and Section 10.3.4 for further details.
- 15 Patients who experience a delay in the administration of BNT411 should return to the clinic at least every 2 weeks (±3 days) and assessments listed under 'unscheduled visit' should be performed and reported in the eCRF. Unscheduled visit assessments should be performed at the investigator's discretion. For information on COVID-19 vaccination during the trial, see Section 10.9.
- 16 All labs at the screening visit must be obtained within 7 days of Cycle 1 Day 1. All lab assessments except for PK and biomarkers are done locally.
- 17 Laboratory samples should be obtained up to 3 days before treatment administration.
- 18 TSH, free-T3 and free-T4 will only be measured at screening, Cycle 1 Day 1, Cycle 2 Day 1, and on Day 1 of every evenly numbered cycle thereafter.
- 19 Serum pregnancy test is performed at screening. Thereafter, urine pregnancy test is sufficient unless indicated otherwise. The frequency of testing during treatment phase may depend on clinical indication per investigator's assessment and may also depend on local guidelines and regulations.

- 20 Medical history includes cancer history.
- 21 Prior/Concomitant Medications and Non-Drug Therapies include all anti-cancer pre-treatments.
- 22 Prior/Concomitant Medication and Non-Drug therapies only for BNT411 related AEs.

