## 8.7.1 Time Period and Frequency for Collecting AE and SAE Information

All SAEs and AEs will be collected from the signing of the ICF until the safety follow-up visit at the time points specified in the SoA (Section 1.3, Table 1-5).

All SAEs will be recorded and reported by the investigator to the sponsor or designee immediately and no later **than 24 hours after becoming aware of the event**, as indicated in Section 10.3.

Investigators are not obligated to actively seek AE or SAE information after conclusion of the trial participation. However, if the investigator learns of any SAE, including a death, at any time after a patient has been discharged from the trial, and he/she considers the event to be reasonably related to the trial treatment or trial participation, the investigator must promptly notify the sponsor.

Safety-related information / paper-based SAE reports (initial and follow-up reports) are to be sent to the safety contact details outlined in Section 10.3.4.

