#### **Period of observation:**

- The period of observation starts after informed consent has been obtained. After informed consent, all AEs and SAEs should be reported until 60 days after the last dose of trial treatment.
- AEs occurring later than 60 days after the last trial treatment must only be documented if a relationship to trial treatment or trial procedure is suspected.

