#### **AE and SAE Recording**

- SAEs will continue to be reported until 60 days after the last dose of IMP. All SAEs for which the investigator suspects a relationship to IMP or trial procedure have to be reported to the safety contact (given in Section 10.3.4), even if they occur after the end of the period of observation. In Germany, all SAEs, regardless of relatedness, that occur in a patient throughout his or her lifetime should be reported (Section 12.2.1).
- Investigators will seek information on AEs at each subject contact. All AEs, whether reported by the subject or noted by trial personnel, will be recorded in the subject's medical record and on the AE eCRF.
- The investigator should follow each AE until the event has resolved to baseline grade
  or better, the event is assessed as stable by the investigator, the subject is lost to followup, or the subject withdraws consent. Every effort should be made to follow all SAEs
  considered to be related to trial treatment or trial-related procedures until a final
  outcome can be reported.

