8.5.2 Adverse events

This section includes the description of the analysis planned for the primary endpoints on this trial.

AEs will be coded using the most recent version of Medical Dictionary for Regulatory Activities (MedDRA®) coding system version 26.0 or higher to get a SOC and PT for each AE and graded for severity using NCI CTCAE v5.0. In case a patient has an AE with missing relationship status, the event will be assumed to be related and associated with the treatment received in the summaries (will be listed as collected in the listings). No imputation for missing NCI-CTC grades will be performed.

A treatment-emergent AE (TEAE) is defined as any AE with an onset date on or after the first administration of trial treatment (BNT411 in part1A and BNT411, atezolizumab, carboplatin, and etoposide in Part 1B) (if the AE was absent before the first administration of trial treatment) or worsened after the first administration of trial treatment (if the AE was present before the first administration of trial treatment). AEs with an onset date more than 60 days after the last administration of trial treatment will be considered as treatment-emergent only if assessed as related to trial treatment (BNT411 for Part 1A and BNT411, atezolizumab, carboplatin, and etoposide for Part 1B) by the investigator.

Treatment-emergent AEs will be summarized by cohort and trial part and total within trial part. In addition, treatment-related TEAEs will be summarized by cohort and trial treatment (BNT411, atezolizumab, carboplatin, and etoposide) within trial part.

Only TEAE data will be summarized for the Safety set for each trial part (Part 1A and Part 1B). Non-TEAEs will be listed only.

Dose-limiting toxicities

In general, a DLT for a drug or other treatment is defined as one or more AEs that prevents an increase of the dose level of that treatment (for details on dose escalation decision rules see Appendix 5).

Serious AEs (SAEs), non-serious grade ≥ 3 AEs and clinically significant abnormal laboratory values grade ≥ 3 will be collected and assessed for DLTs (for each dose level during the first cycle). Common Terminology Criteria for Adverse Events (NCI CTCAE) v.5.0 will be used to grade the intensity of AEs.

More details regarding DLTs can be found in the Section 6.6 of the CTP.

For the additional rules and considerations of MTD and RP2D other than what was already defined in Section 1.1, see Section 4.1.1.2 of the CTP.

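### When a patient starts new anti-cancer therapy within 60 days of the last dose, the protocol's AE collection rules conflict with one another and with the 60-day TEAE count

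*Protocol*

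**What the plan says.** Two sets of rules cover the time between a switch to new therapy and Day 60 after the last dose.

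**Rules that let collection narrow at the switch**
- Protocol 7.2.2, for a patient who switches within 60 days: "the safety follow-up visit should be performed prior to starting new anti-cancer treatment". It continues: "Once new anti-cancer treatment is initiated, the patient will move into survival follow-up".
- Protocol 8.7.1: "All SAEs and AEs will be collected from the signing of the ICF until the safety follow-up visit".
- In survival follow-up, Table 1-1 footnote 14 reads "Suspected BNT411-related AEs only". Table 1-5 adds procedure-related AEs in all countries. Spain and Germany add AEs related to atezolizumab, carboplatin or etoposide, and Germany also adds every SAE.

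**Rules that keep collection open to Day 60**
- Protocol 10.3.3, under the period of observation: "all AEs and SAEs should be reported until 60 days after the last dose of trial treatment". No exception is made for new therapy.
- Footnote 13 of Tables 1-1 and 1-2 gives the same 60 days. In Part 1B it runs from the last dose of whichever of the four drugs ends latest.
- Footnote 2 of both tables: "Survival follow-up starts after all other protocol required visits have been completed".

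**What is counted.** SAP 8.5.2 says "AEs with an onset date more than 60 days after the last administration of trial treatment will be considered as treatment-emergent only if" they are judged related, and Protocol 9.4.2 has the same rule. Every AE up to Day 60 therefore counts whatever its cause, and new therapy does not end the count. SAP 8.1 divides AE percentages by all patients in the analysis set. SAP 8.6.3 only lists new anti-cancer treatment.

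**SAE window in Part 1B.** Elsewhere in 10.3.3: "SAEs will continue to be reported until 60 days after the last dose of IMP". Protocol 6.1 treats only BNT411 as an IMP in the USA and UK, but all four drugs as IMPs in Spain and Germany.

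**The concern.** TEAEs, including grade 3 or higher, serious and fatal ones, are primary endpoints. For a patient who switches early, whether an unrelated event between the switch and Day 60 is recorded depends on which section the site follows. A site working from 7.2.2 and 8.7.1 may stop recording unrelated AEs. A site working from 10.3.3 continues, and also records events that arise on the next therapy. The SAP pools both kinds of record in one numerator over one denominator and does not mention the difference.

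Country adds a further difference. SAP 8.5.2 tabulates related TEAEs separately for BNT411, atezolizumab, carboplatin and etoposide. After a move to survival follow-up, Table 1-5 asks for events related to the last three only in Spain and Germany. The SAE rule tied to the last IMP differs between countries in the same way.

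**Working it through.** The plan gives no figure to reproduce here: it tests no hypotheses and states no switch rate. The check sets the rules side by side and then illustrates the possible size.

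**1. One patient under both rules.** Take the last dose as Day 0, new therapy on Day 21, and a first unrelated, non-serious grade 3 AE on Day 40.

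| Rule followed | AE recorded? | Counted as grade 3 or higher TEAE? | In denominator? |
|---|---|---|---|
| 7.2.2 with 8.7.1, Table 1-5 and footnote 14 | No | No | Yes |
| 10.3.3 with footnote 13 | Yes | Yes (Day 40 is within 60) | Yes |

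Both sites can point to protocol text. If the event were serious, a German site would record it under either rule. If it were BNT411-related or procedure-related, every site would.

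**2. Days in dispute.** For a switch on Day s the disputed period is 60 − s days:
- Day 14: 46 days (76.7%)
- Day 21: 39 days (65.0%)
- Day 30: 30 days (50.0%)
- Day 45: 15 days (25.0%)

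**3. Possible shortfall if every site narrows collection at the switch.** The inputs are assumptions, not document figures:
- q: probability of a first unrelated event of a given category in the 60 days
- f: share of patients who switch
- s: switch day
- constant hazard h = −ln(1 − q)/60

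Reported rate = (1 − f)q + f(1 − exp(−h·s)).

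Example with q = 20%, f = 50%, s = 14: h = 0.2231/60 = 0.00372; 1 − exp(−0.0521) = 0.0507; reported = 0.5 × 0.20 + 0.5 × 0.0507 = 0.1254. The shortfall is 7.5 percentage points.

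| q | f | s = 14 | s = 30 | s = 45 |
|---|---|---|---|---|
| 10% | 20% | 1.5 | 1.0 | 0.5 |
| 10% | 50% | 3.8 | 2.4 | 1.2 |
| 20% | 20% | 3.0 | 1.9 | 0.9 |
| 20% | 50% | 7.5 | 4.7 | 2.3 |
| 40% | 20% | 5.8 | 3.5 | 1.6 |
| 40% | 50% | 14.4 | 8.7 | 4.1 |

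These shortfalls apply to patients with no earlier event in the category, because SAP 8.5.2 counts patients with at least one event. For a whole cohort they shrink in proportion to the share of such patients. If every site follows 10.3.3, the shortfall is 0.

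**4. Cohort size.** One patient recorded differently moves a cohort percentage by 100/3 = 33.3 points, 100/6 = 16.7 points, or 100/14 = 7.1 points in a cohort backfilled to its limit.

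**5. SAE window in Part 1B.** Suppose atezolizumab runs three 21-day cycles (63 days) beyond the last BNT411 dose. In the USA or UK, the IMP wording ends general SAE reporting on Day 60 after BNT411. The period-of-observation text, Table 1-2 footnote 13 and the SAP all end it on Day 63 + 60 = 123.

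**The case against.** The strongest reply is that 7.2.2 only schedules visits. It never says AE recording stops, Section 8.7 refers recording to 10.3, and 10.3.3 is explicit about 60 days. The amendment log for Version 3.0 also records that an SAE exemption for events after another anti-cancer therapy was deleted, which fits an intention to keep such events. This supports 10.3.3 as the intended rule, and the fix follows it. It does not remove the conflict: Table 1-5 sets collection by trial phase, 7.2.2 sets the phase, and 8.7.1, the section on the AE collection period, ends it at a visit that 7.2.2 moves earlier.

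Footnote 2 need not contradict 7.2.2. If the early visit counts as the last required one, the two agree. The footnote needs clarifying and is not the main evidence.

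On the IMP wording, the reply is that the period-of-observation text already covers a patient who continues atezolizumab, and that the log shows IMP was kept there on purpose. Both are true, but two different end dates then stand in one section.

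A reader might infer more than the documents support:
- **That switchers are counted as event-free over days nobody observed.** Related and procedure-related AEs and deaths are still collected, as are all SAEs in Germany, and 10.3.3 requires everything to Day 60. A patient with an earlier event in the category is already counted.
- **That the RP2D is distorted.** Escalation and the MTD rest on DLTs in the 21-day first cycle. For other toxicities, Protocol 4.1.1.2 gives weight to BNT411-related AEs, which are collected under either rule. SAP 8.1 plans no formal cohort comparisons, and nothing in the documents shows that switch timing differs by cohort or tumor type.
- **That a share of lost days measures bias.** If 25% to 50% of patients switched evenly between Day 14 and Day 60 (mean Day 37), 23/60 × 25% to 50% = 9.6% to 19.2% of post-treatment days would be in dispute. That rests on assumed rates, leaves out all on-treatment time, and is not an error in any endpoint.

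**Conclusion.** The inconsistency is real and should be corrected. The protocol gives two answers on whether unrelated AEs are collected between a switch and Day 60. The SAP counts the whole 60 days over all patients without saying which answer it assumes.

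The exposed outputs are the all-causality summaries of any TEAE, grade 3 or higher TEAE and serious TEAE, for patients whose first such event falls after the switch. In Part 1B in the USA and UK, events related only to atezolizumab, carboplatin or etoposide are exposed as well. DLT and MTD decisions are untouched, and BNT411-related summaries are largely protected.

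The size cannot be stated, because it depends on switch rates, switch timing and site practice, none of which the documents give. Under the assumptions shown, the shortfall runs from 0 (all sites follow 10.3.3) to 14.4 points (q = 40%, half of patients switching on Day 14, all sites narrowing collection, no earlier events).

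**What to change.** 1. **Align collection.** Reconcile Protocol 7.2.2, 8.7.1, Table 1-5 and footnotes 2 and 14 of Tables 1-1 and 1-2 with 10.3.3 and footnote 13. All AEs and SAEs would then be collected for the 60 days that the TEAE definition counts, whether or not new therapy starts, and the restricted collection would begin only after that.
2. **Align the SAE window.** In the 10.3.3 sentence on continued SAE reporting, replace IMP with trial treatment. The Part 1B window then matches the period-of-observation text, footnote 13 and the SAP in every country.
3. **Keep the 60-day TEAE definition as the main analysis.** Cutting the main window at the switch would leave patients with unequal follow-up over the same denominator.
4. **Add a supplementary summary to SAP 8.5.2.** Cut it at the day before new anti-cancer therapy and keep later events only if related to trial treatment. Do not use the SAP 8.1 imputation to exclude events. That rule sets a missing start date, or a partial one that fits, to the end-of-treatment visit, and as a cut-off it could drop real events from nearly all of the 60 days.

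The cost is protocol and SAP wording, a little more data collection after a switch, and one extra set of tables.

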# 7.3 Lost to Follow up

For patients whose status is unclear because they fail to appear for trial visits without stating an intention to withdraw consent, the investigator should show "due diligence" by contacting the patient, family or family physician as agreed in the informed consent form and by documenting in the source documents steps taken to contact the patient, e.g. dates of telephone calls, registered letters, etc. A patient should not be considered lost to follow-up until due diligence has been completed (where possible, three telephone calls and, if necessary, a certified letter to the patient's last known mailing address or local equivalent methods). Patients lost to follow-up should be recorded as such on the appropriate disposition eCRF.

#### **8 Trial Assessments and Procedures**

- Trial procedures and their timing are summarized in the SoA. Protocol waivers or exemptions are not allowed.
- Immediate safety concerns should be discussed with the sponsor immediately upon occurrence or awareness to determine if the patient should continue or discontinue trial treatment.
- Adherence to the trial design requirements, including those specified in the SoA, is essential and required for trial conduct.
- All screening evaluations must be completed and reviewed to confirm that potential
  patients meet all eligibility criteria. The investigator will maintain a screening log to
  record details of all patients screened and to confirm eligibility or record reasons for
  screening failure, as applicable.
- Procedures conducted as part of the patient's routine clinical management (e.g. blood count) and obtained before signing of the ICF may be utilized for screening or baseline purposes provided the procedures met the protocol-specified criteria and were performed within the time frame defined in the SoA.
- In case the COVID-19 pandemic creates challenges that may interfere with the conduct of this clinical trial, the addendum "Clinical trial protocol addendum related to COVID-19 pandemic Version 3.0 04 Jun 2021" gives guidance and outlines assistance on protocol procedures, patient enrollment and requirements within the established protocol.
- Information relating to COVID-19 vaccinations including a risk-benefit assessment and guidance for vaccination during this clinical trial is provided in Sections 10.8 and 10.9.

The schedule of assessments to be performed in Parts 1A and 1B of the trial are summarized in Table 1-1 to Table 1-8 in Section 1.3.1. With the exception of post-dose blood and urine sampling for PK assessments, all assessments should be performed before trial treatment administration (on the applicable days) or any planned intervention. On the days of tumor imaging, blood sampling can be before or after imaging assessments.

